## **Distress protocol**

If any participant shows emotional distress or anxiety during one of the study visits, the examiner will follow the protocol outlined below to ensure the safety of the research participant.

The assessment appointment will be stopped. Distressed participants will be invited to take a break in the private side clinic of the Prosthetics Department in the School of Dentistry, Belfast, and, if appropriate, to discuss their concerns or worries with the examiner, a family member, or friend. A senior clinician (one of the Restorative Dentistry Consultants) may also be invited into the side room. The participant will be supported to recommence the assessment if they decide to do so. Alternatively, the assessment may be rearranged. Any participant has the right to withdraw from the study at any time and those who do not wish to continue will be provided with the contact details of the research team and relevant support agencies (e.g. their GP or Macmillan Cancer Support).

In all instances, participants will be encouraged to contact their oncologist, their dentist, or their GP if they have any further worries or concerns about their participation in the study.

Where appropriate, a resolution will be found. This may involve simply reassuring the patient or offering remedying treatment where appropriate. Remedying treatment may include (in line with current clinical practice):

- Management of dry mouth (e.g. through the use of saliva substitutes, constant sips of water).
- Management of toothache (e.g. through root canal treatment, dental extraction).
- Management of limited mouth opening (e.g. through the use of a Therabite device, jaw exercises).
- Management of osteoradionecrosis (e.g. oral surgery/maxillofacial surgery referral, pharmacological measures).

## **Calibration of examiners**

Two qualified dentists will act as examiners for the study. They will undertake all of the pre- and post-radiotherapy dental assessments. The examiners are already employed within the School of Dentistry, Belfast, Belfast Health and Social Care Trust. Both dentists will undergo calibration prior to the commencement of the study (approximately 3 months beforehand).

The calibration session will re-educate examiners on the processes involved in the clinical assessment of head and neck radiotherapy patients. This will be led by Consultants in Restorative Dentistry. The calibration session will be undertaken outside of Belfast Health and Social Care Trust normal working hours and will be accredited as a 'Continual Professional Development' study session for both examiners. Topics to be covered include: dental caries assessment, periodontal assessment, measurement of stimulated salivary flow rate, ruler measurement of mouth opening, prescribing of dental radiographs, pre- and post-radiotherapy dental extractions, and instructing patients on oral hygiene, denture hygiene, and diet.

Inter-examiner consistency regarding the assessment of dental caries and the assessment of periodontal disease indices will be determined via a series of clinical photographs, radiographs, and artificial phantom-heads in the Clinical Teaching Lab, 2nd floor, School of Dentistry, Belfast. Agreement between examiners will be determined by the calculation of the kappa statistic. The target level of agreement will be 0.81-1.00

(almost perfect agreement). Where there are major discrepancies, inter-examiner differences will be reviewed and resolved by group discussion.

Both examiners are currently involved in the pre- and post-radiotherapy dental assessment of head and neck cancer patients in the Prosthetics Department, School of Dentistry, Belfast, as part of their current job role. They already undertake dental caries and periodontal disease indices assessments, as well as the ruler measurement of mouth opening and the determination of salivary flow rates, on a day-day basis.

## **Spreadsheets**

Separate password-protected spreadsheets will be created on an encrypted password-protected Queen's University computer/laptop as follows:

1. Four clinical data spreadsheets containing patients' anonymous codes alongside data from their clinical assessment (caries, periodontal assessment, stimulated salivary flow, mouth opening, questionnaire results). This data will be input by one of the dental examiners within the private side clinic in the Prosthetics Department of the School of Dentistry, Belfast, after each clinical session has ended. There will be one spreadsheet for each of the four dental assessment appointments.
2. A radiotherapy dose spreadsheet containing patients' 'unique identifiers' alongside their radiotherapy dose data (dose to teeth, dose to spared parotid gland, location of the tumour). This will be input by the dental examiner tasked with contouring teeth on each patient's radiotherapy planning CT scan.

The following information will be retained securely within the Trust (via a Belfast Health and Social Care Trust computer) and with password-protected access:

1. A list of patients' H&C and Dental Health numbers alongside their anonymous codes. To be stored by the applicant fellow.
2. A list of patients' H&C numbers alongside their CT scan 'unique identifiers'. To be stored by a member of the clinical radiotherapy team on a Belfast Health and Social Care Trust computer.

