## **Protocol for post radiotherapy dental assessments**

Participants will be followed-up at 6 months, 12 months, and 24 months post-radiotherapy.

Patients will undergo dental assessment on a Wednesday morning or afternoon in the Prosthetics Department of the School of Dentistry, Belfast. The following measurements will be collected (using the same methods and examiners outlined above): charting of dental caries, 6-point clinical attachment loss and probing pocket depth charting, stimulated salivary flow rate, mouth opening, oral hygiene practice, dietary assessment, quality of life, patient reported xerostomia, micro-costings study.

N.B. – For each patient, all efforts must be made to ensure that saliva collection is undertaken at a similar time of day for each of the four dental assessment appointments (i.e. the pre-radiotherapy assessment appointment and the three post-radiotherapy assessment appointments). This is due to the diurnal variation in saliva production. Patients will be asked to refrain from smoking, eating and drinking, and other forms of oral stimulation (e.g. oral hygiene) 90 minutes prior to the collection of saliva at post-radiotherapy assessment appointments. These instructions will be explained and provided in writing, and attached with the post-radiotherapy assessment appointment letter as a reminder to patients.

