## **Radiation dose and tumour location determination**

Patients will receive radiotherapy as prescribed by their Consultant Clinical Oncologist. The Clinical Oncologist will also plan individual tissue exposures in line with current practice. There will be no alteration or experimentation with radiotherapy dose or the radiotherapy treatment plan for the purposes of conducting this research study.

Using additional research software (Non-Clinical Eclipse System by Varian Medical Systems UK Ltd), radiation dose exposures to the teeth and 'spared' parotid gland will be calculated after the teeth and parotid glands have been contoured on each patient's radiotherapy planning CT scan. The Clinical Oncologist will contour the parotid glands in line with current practice. A dentist will contour the teeth on patient-anonymised CT scans. Tumour location will be determined from the initial referral letter sent by the Head and Neck Cancer Multidisciplinary Team.

The dentist will be blinded to patient details when contouring teeth on CT scans. A 'unique identifier' will be generated for each patient's CT scan. A member of the clinical radiotherapy team (not involved in the study) will securely store a list of patients' 'unique identifiers' and H&C numbers on a Belfast Health and Social Care Trust computer. The dentist will then input radiation dose data (doses to the teeth and to the 'spared' parotid gland) alongside each patient's 'unique identifier' onto a separate password-protected spreadsheet stored on an encrypted password-protected Centre for Public Health, Queen's University Belfast computer.

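### One of the two outcome examiners also contours the teeth and enters dose and tumour location, and the plan's blinding covers neither the tumour-location entry nor the scoring of caries and periodontal disease

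*Combined protocol and SAP*

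**What the plan says.** Calibration of examiners sets the number of outcome assessors: "Two qualified dentists will act as examiners for the study". It adds: "They will undertake all of the pre- and post-radiotherapy dental assessments". The section on post-radiotherapy assessments keeps the same people at 6, 12 and 24 months ("using the same methods and examiners outlined above").

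Radiation dose and tumour location determination gives the contouring task to a dentist and states: "The dentist will be blinded to patient details when contouring teeth on CT scans". Scans are anonymised, each has its own CT identifier, and the link to the patient is held elsewhere: "A member of the clinical radiotherapy team (not involved in the study) will securely store a list of patients' 'unique identifiers' and H&C numbers". On tumour site the section says: "Tumour location will be determined from the initial referral letter sent by the Head and Neck Cancer Multidisciplinary Team". When it lists what the dentist types into the dose file, it names only the tooth and parotid doses.

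Spreadsheets, item 2, lists the content of the same file as "dose to teeth, dose to spared parotid gland, location of the tumour", stored against the CT identifier, and says who fills it in: "This will be input by the dental examiner tasked with contouring teeth on each patient's radiotherapy planning CT scan". Item 1 has one of the dental examiners type in the outcome data, under a different anonymous code.

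**The concern.** The radiation section, read alone, leaves room for an independent dentist to do the contouring. The Spreadsheets section removes that room: the person who measures the exposure is one of only two people who score the outcome.

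Both primary outcomes involve examiner judgement: caries by mirror, probe and light, and periodontal disease by probing against millimetre cut-offs. The clinical hypothesis is directional, with more dose expected to mean more disease. An examiner who knows a patient's dose could, without intending to, resolve borderline findings in that direction. That would produce a dose association from scoring alone. The covariates listed under Statistical analysis could not remove it, because knowledge of dose is not among them and is not recorded.

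**Working it through.** **Step 1. The data flow.** Setting the sections side by side:

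| Question | Radiation dose section | Spreadsheets, item 2 |
|---|---|---|
| Who contours and enters dose? | A dentist | The dental examiner who contours |
| What does that person enter? | Tooth and parotid doses | Those doses plus tumour location |
| Against which label? | CT identifier | CT identifier |
| Where does tumour location come from? | The patient's referral letter | Not stated |

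A referral letter concerns a known patient; a CT identifier is meant to be unlinked from one. To put the first on the row of the second, somebody must make the link. The plan names the examiner as the person who enters it and gives no intermediate step. If the examiner makes the link, the same row shows that patient's tooth and parotid doses.

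**Step 2. What the blinding covers.** The promise is limited to patient details during contouring. I found no statement that examiners are masked to dose when scoring, no timing of contouring or dose extraction relative to the 6, 12 and 24 month examinations, and no rule that the contouring examiner does not score the same patients.

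**Step 3. The plan's own figures.** Inputs from Sample size: 150 evaluable patients, an 80%/20% split (120 and 30), SD 4.0, target difference 3.0 teeth, 5% level (taken as two-sided, which the plan does not state).

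- SE of the difference = 4.0 × √(1/30 + 1/120) = 0.816 teeth.
- 3.0 / 0.816 = 3.67, which gives power of 95.7% (normal) or 95.5% (t distribution). The stated power of over 80% is correct.
- 150 / 0.70 = 214.3, rounded up to 215, as stated.

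Nothing in this point disputes these figures.

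**Step 4. Illustration of scoring bias.** Suppose there is no true difference, and exposure-aware scoring adds *b* carious teeth in one dose group relative to the other. The t-test then rejects as if the true difference were *b*, with noncentrality *b* / 0.816. If only half the examinations are aware, the average shift is *b*/2. Neither *b* nor the aware share is in the documents; both are assumptions.

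| Assumed *b* (teeth) | *b* / 0.816 | False-positive rate, all aware | False-positive rate, half aware |
|---|---|---|---|
| 0.25 | 0.31 | 6.1% | 5.3% |
| 0.5 | 0.61 | 9.3% | 6.1% |
| 1.0 | 1.22 | 22.9% | 9.3% |
| 1.5 | 1.84 | 44.6% | 15.0% |

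A shift of 1.0 tooth is one third of the 3.0-tooth target. The half-aware column corresponds to one contouring examiner who does half the charts; the plan does not give the division of work. The periodontal outcome is not quantified here.

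**The case against.** A reader might infer that the stated blinding must fail. The documents do not support that. The promise concerns contouring only, and it is backed by anonymised scans, separate identifiers and a key held by someone outside the study. Contouring can be blind as described. The plan also does not say who reads the referral letter, and the key holder could pass on the site already coded to the CT identifier. What stands is an inconsistency between two sections with an unstated route, not a demonstrated break.

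A reader might also infer that the examiner would recognise on CT a dentition already charted in clinic. That is possible, but nothing in the documents shows that an anonymised scan could be matched to one of 215 recruits, and the point does not rest on it.

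Scoring is structured: WHO and ICDAS criteria, millimetre thresholds, recorded radiographic evidence of caries, and a kappa target of 0.81-1.00. These limit discretion. They do not detect awareness bias: the kappa exercise takes place before the study on photographs, radiographs and phantom heads, and the same examiners read the patients' radiographs.

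Finally, full masking may be out of reach. The examiners work in the clinic that receives the referrals, so they may know tumour site from care. The post-radiotherapy extraction guidance also lists radiation dose to the jaws among the factors to consider. This is fair, and it limits what the fix can promise. It does not justify leaving the avoidable route open.

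**Conclusion.** The point holds in a limited form. One of two outcome examiners also measures the exposure. The two sections disagree on whether that person handles tumour location, and the version that includes it is not reconciled with the blinding statement. Outcome scoring is not stated to be masked to dose, and dose extraction is not timed after follow-up. This is an open route for bias, not evidence that bias will occur.

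Its size cannot be derived from the documents. For assumed shifts of 0.5 to 1.0 tooth, the nominal 5% error rate becomes about 9% to 23% if every examination is aware, and about 6% to 9% if half are. These figures rest on the plan's SD and group split, a two-sided t-test and no true difference. The higher pair should not be read as expected, since the plan describes one contouring examiner out of two. The weakness should be corrected because doing so is cheap; it does not invalidate the design.

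**What to change.** 1. Contour the teeth and extract doses for each patient only after that patient's 24-month chart is entered and locked (for a patient who leaves early, after the last chart). The planning CT already exists and the dose work uses separate research software, so no scan information is lost and treatment planning is untouched.
2. Have the radiotherapy team member who holds the key supply tumour location already coded to the CT identifier. This matters more once contouring follows the outcome charts, because it also helps keep contouring blind to outcome.
3. Reconcile the radiation dose section with Spreadsheets, item 2, on who enters what.
4. State that examiners are masked to tooth and parotid dose at each assessment where feasible, and state as a limitation that they may know tumour site, and jaw dose, from clinical care.

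The cost is protocol wording and a change in task order. Dose data arrive later, and the key holder, now described as not involved in the study, takes on a small task that the wording should acknowledge. Giving every follow-up chart to the non-contouring examiner would also separate the roles, but it changes the staffing plan and is not needed if step 1 is adopted.
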